2.3 Benefit/Risk Assessment

As of 31 July 2021, 2,041 male and female participants in 16 completed and 4 ongoing clinical studies have been exposed to evobrutinib including healthy participants, participants with RMS, systemic lupus erythematosus, or rheumatoid arthritis, and participants with renal impairment. Evobrutinib was generally safe and well tolerated in all participants. The TEAEs have been primarily mild to moderate in severity. Two Phase III studies with evobrutinib in patients with RMS (MS200527_0080 and MS200527_0082) are currently ongoing.

The evobrutinib treatment duration in this study will be 14 days in total, with 45 mg twice daily dosing of evobrutinib under fed conditions (see Section 4.3). CCI

More detailed information about the known and expected benefits and risks and reasonably expected adverse events of evobrutinib may be found in the IB.

Based on the available nonclinical and clinical data to date, the conduct of the study, as specified in this protocol, is considered justifiable.

2.3.1 Risk Assessment

Identified and Potential Risks of Clinical Significance	Summary of Data/Rationale for Risk	Mitigation Strategy
Study Intervention(s) Evobrutinib		
Identified risk: Elevated liver transaminases	Elevated liver transaminases have been observed in patients treated with evobrutinib across the program and is considered an important identified risk (for details refer to current IB Section 6.1). Elevations of liver transaminases were frequent, generally mild (Grade 1), asymptomatic and reversible, and occurred within 6 months of treatment. However, more severe cases were reported. This has not been observed in healthy participants after a single dose nor in patients receiving short treatment with evobrutinib.	Participants with known history of hepatic disorder will not be included in the study. Study participants will be confined, and liver tests will be monitored during the study.
CCI [REDACTED] [REDACTED]	[REDACTED]	Only female participants who are not of childbearing potential are eligible for participating in the study (see Section 5.1).
Study Intervention(s) EE/NET		
Potential risk: Cardiovascular disease	There is a risk of serious cardiovascular events from COC use. This risk is known to increase with age, particularly in women over 35 years of age, and with the number of cigarettes smoked.	Only nonsmokers will be enrolled, and only 2 doses of COC (separated by 2 weeks) will be administered.
Potential risk: Cardiovascular disease	The use of COC increases the risk of venous thromboembolism. The risk of venous thromboembolism in women using COCs is estimated to be around 3 to 9 per 10,000 woman-years. The risk is highest during the first year of use of a therapy. Use of COCs also increases the risk of cardiovascular events such as strokes and myocardial infarctions, especially in women with other risk factors for these events. The risk of thromboembolic disease due to oral contraceptives gradually disappears after the use is discontinued.	Women with a history of, or current, deep vein thrombosis or pulmonary embolism, cerebrovascular disease, coronary artery disease, cardiac valvular disease, uncontrolled hypertension, headaches with focal neurological symptoms, diabetes mellitus or atrial fibrillation will be excluded from the study.
Potential risk: breast, ovarian, endometrial, cervical and other estrogen- or progestin-sensitive cancer	Most cancers of the female reproductive system are estrogen- or progestin-sensitive cancers and the use of COCs therefore potentially stimulates further growth-expansion.	Women with a history of, or current, breast, endometrial, cervical or other estrogen- or progestin-sensitive neoplastic disease, as well as undiagnosed abnormal uterine bleeding, will be excluded from the study.

Identified and Potential Risks of Clinical Significance	Summary of Data/Rationale for Risk	Mitigation Strategy
Study Procedures		
Blood draw	Blood draws have the potential to cause AEs such as fainting or hematoma.	Amount of blood drawn will be strictly controlled. Participants will be in a hospital setting with support from highly trained professionals.
ECG	Contact allergies can develop during ECG procedures.	Participants with known contact allergies will not be included in the study.
Other		
Not applicable		

AE = adverse events; COC = combined oral contraceptive; ECG = electrocardiogram; EE/NET = ethynodiol/norethisterone.

2.3.1.1 Potential Risks Associated With the COVID-19 Pandemic Situation

As for the general population, there is a risk of a SARS-CoV-2 infection for study participants as long as the COVID-19 pandemic situation is ongoing.

Evobrutinib is a BTK inhibitor and, as such, works as an immunomodulator. There was some decrease in immunoglobulin M, an increase in immunoglobulin A, and some modest changes in immunoglobulin G following long-term treatment with evobrutinib; these changes were not clinically significant. In addition, duration of the evobrutinib treatment in this study will be limited to 14 days. Although BTK is not required to clear viral infections, apart from enteroviruses, no information is available regarding BTK inhibitors as a class or evobrutinib specifically regarding the risk for either contracting SARS-CoV-2 or severity of COVID-19 at this point. The published data on approved BTK inhibitors (e.g., ibrutinib and acalabrutinib) used in oncology suggest a protective effect of BTK inhibitors for severity and mortality of COVID-19 (Scarfò 2020; Thibaud 2020; Treon 2020).

During the entire study, all recommendations issued by the Robert Koch Institute as well as local guidelines with respect to the minimization of the risk of disease spreading, e.g., social distancing, disinfection, hygiene, and wearing of mouth-nose masks will be followed. During the pandemic situation, further measures according to recommendations and requirements from local health authorities may become necessary and will be followed within the context of this study as far as applicable, to ensure full implementation of the principles of GCP with priority on participant safety in this study also during the COVID-19 pandemic situation. These measures are described in a preventive action plan implemented at the Investigator site.

Due to the constantly evolving nature of the COVID-19 pandemic, the most up-to-date guidelines from the Robert Koch Institute and the applicable federal/local guidelines will be followed. In addition, to minimize the risk coming from a current infection and the risk of getting infected by other participants during the in-house phase (covering the whole treatment phase) of the study, the following measures are implemented:

- Only participants without any symptoms of a respiratory disease and without contact to any known SARS-CoV-2 positive patient or COVID-19 patient will be included into the study.
- Furthermore, as a part of the clinical study procedures, participants will be closely monitored (including for signs of COVID-19) during the entire study duration.
- Continuation of the study in case of a SARS-CoV-2 infection in the study participant or an identified contact to a SARS-CoV-2 positive participant or COVID-19 patient will be done at the Investigator's discretion and agreement with the medical monitoring team.
- The Sponsor will monitor the events related to any SARS-CoV-2 infection reported following evobrutinib regularly and update the recommendations, if necessary.

2.3.2 Benefit Assessment

Healthy participants may expect no direct benefit from participating in clinical studies with evobrutinib.

2.3.3 Overall Benefit: Risk Conclusion

Risk minimization measures routinely implemented in early phase clinical studies are considered adequate, including exclusion criteria (see Section 5.2), close biochemical and hematology laboratory monitoring (see Section 8.2.4), and observation of vital signs and ECGs (see Sections 8.2.2 and 8.2.3). Evobrutinib will be discontinued in case of events that unacceptably endanger the safety of the participant (see Section 7). Participants will be admitted to the study site for the duration of the study to allow continuous safety monitoring.

Considering the measures taken to minimize the risk to participants in this study, the potential risks identified in association with evobrutinib and EE/NET are justified in healthy participants.

3 Objectives and Endpoints

Objectives	Endpoints	Ref. #
Primary		
To investigate the effect of multiple doses of evobrutinib on EE/NET PK in healthy participants	Plasma EE/NET: AUC _{0-∞} C _{max}	1
Secondary		
To assess the safety and tolerability of evobrutinib when administered together with EE/NET in healthy participants	Nature, occurrence, and severity of TEAEs	2
	Absolute values and changes in safety laboratory tests	3
	Single 12-lead ECGs evaluated by Investigator	4
	Vital signs assessed from time of first dose to end of study participation	5
	Plasma EE/NET:	6

Objectives	Endpoints	Ref. #
To characterize the effect of evobrutinib on EE/NET PK	t_{max} $t_{1/2}$ $AUC_{0-t_{last}}$ CL/F VZ/F	

CCI

ECG=electrocardiogram; EE/NET= ethinyl estradiol/norethindrone; PK=pharmacokinetics; TEAE=treatment-emergent adverse event.

4 Study Design

4.1 Overall Design

Study Design	Open-Label, Multiple-Dose Study of the Effect of Evobrutinib on the Pharmacokinetics of a Combined Oral Contraceptive in Healthy Female Participants (see Section 1.2)
Control Method	None (uncontrolled)
Single or Multicenter	Single center
Control Group	Not applicable
Study Population Type	Healthy female participants not of childbearing potential (see Section 5)
Level and Method of Blinding	Open-label
Bias Minimization Method(s)	Not applicable
Study Intervention Assignment Method	Not applicable

Involvement of Special Committee(s)	No
Total Duration of Study Participation per Participant	Up to 46 days (see Section 1.3)
Provisions for Study Extension or Entry into Roll-Over Studies	None
Adaptive Aspects of Study Design	Not applicable

4.2 Scientific Rationale for Study Design

This single-sequence design is consistent with the FDA guidance for clinical COC DDI study designs and the EMA Guideline on the investigation of drug interactions and allows for adequate characterization of evobrutinib's potential effect on the PK of EE/NET.

4.2.1 Participant Input into Design

Not applicable.

4.3 Justification for Dose

Evobrutinib

The evobrutinib dose to be used in this study, 45 mg twice daily, with each dose to follow a standardized meal, is the same as for Phase III studies evaluating evobrutinib in participants with RMS. This dosing regimen is anticipated to be well tolerated based on prior clinical experience and is adequate to evaluate the potential clinical DDI effect between evobrutinib and EE/NET.

Evobrutinib exposure increased when given with either a high-fat or low-fat meal relative to fasted conditions (see Section 2.2 for details). The exposure in this study is expected to not exceed that of other studies in healthy participants, in which multiple doses up to 200 mg evobrutinib for 14 days were administered and well tolerated.

Ethinyl estradiol/norethisterone

The dose of the COC to be used in this study, 0.03 mg EE/0.5 mg NET, is the same as a commonly used clinical dose for oral contraception in females and similar to the range of those doses used in DDI studies of this type (Zhang 2018).

4.4 End of Study Definition

The end of the study is defined as the date of last contact (related to this study) with the last participant who participates in this study (last participant's Safety Follow-up Assessment/Early Termination Assessment).

A participant has completed the study if she has completed all study parts, including the Safety Follow-up Assessment shown in Section 1.3.

Study termination criteria

The study will be discontinued or terminated if:

- Unacceptable risk, any relevant toxicity, or a negative change in the risk/benefit assessment is identified. This might include the occurrence of AEs which character, severity or frequency is new in comparison to the existing risk profile.
- One serious unexpected AE suspected to be drug related occurs or $\geq 50\%$ of the participants show AEs of at least moderate severity for which a causal relationship to the study intervention or study-related procedures cannot be excluded.
- Any data derived from other clinical trials or toxicological studies become available which negatively influence the risk/benefit assessment.

General information on study termination is specified in [Appendix 2](#).

5 Study Population

The criteria in Sections 5.1 and 5.2 are designed to enroll only participants, who are appropriate for the study; thereby, ensuring the study fulfills its objectives. All relevant medical and nonmedical conditions are considered when deciding whether a participant is suitable for this study.

Prospective approval of protocol deviations to inclusion and exclusion criteria, also known as protocol waivers or exemptions, is not permitted. Minor, not clinically relevant excursions (from the normal range) in laboratory findings are allowed at the discretion of the Investigator (see Section 5.2, #16).

Before performing any study assessments that are not part of the participant's routine medical care, the Investigator will confirm that the participant has provided written informed consent, as indicated in [Appendix 2](#).

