9.4.2 Safety Analyses

All safety analyses will be performed on the Safety Analysis set (see Section 9.3).

Reference #	Endpoint	Statistical Analysis Methods
Primary		
Not Applicable		
Secondary		
2 – Safety	Nature, occurrence, and severity of TEAEs	Adverse event counts and participants with AEs will be summarized for each treatment by SOC and PT. In addition, AEs will be tabulated and listed per participant and analyzed by severity and relationship to study intervention.
3 – Safety	Absolute values and changes in safety laboratory tests	Safety laboratory parameters will be listed for each participant including absolute values and changes from Baseline and flags for measurements outside the reference ranges, if applicable. Laboratory parameters (hematology and clinical chemistry) will be summarized by time point including both absolute values and changes from Baseline.
4 – Safety	Single 12-lead ECGs evaluated by Investigator	Electrocardiogram data will be summarized by absolute values and changes from Baseline values by treatment using descriptive statistics. Clinical noteworthy ECG findings for individual participants will be listed and summarized as appropriate.
5 – Safety	Vital signs assessed from time of first dose to end of study participation	Vital signs by participant, including absolute values and changes from Baseline, will be listed and summarized by treatment and time point using descriptive statistics.
Tertiary/Exploratory		
Not Applicable		

AEs = adverse events; ECG = electrocardiogram; PT = preferred term; TEAE = treatment-emergent adverse events; SOC = system organ class.

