- Medical or scientific judgment will be exercised in deciding whether SAE reporting is appropriate in other situations, such as important medical events that may not be immediately life-threatening or result in death or hospitalization but may jeopardize the participant or may

require medical or surgical intervention to prevent one of the other outcomes listed in the above definition. These events are usually considered as serious.

- Examples of such events include invasive or malignant cancers, intensive treatment in an emergency room or at home for allergic bronchospasm, blood dyscrasias or convulsions that do not result in hospitalization, or development of drug dependency or drug abuse.

Any suspected transmission of an infectious agent via a study intervention is also considered an SAE for reporting purposes, as specified below for reporting SAEs or AESIs.

Recording and Follow-Up of AE and/or SAE

AE and SAE Recording

- When an AE/SAE occurs, it is the responsibility of the Investigator to review all documentation (e.g., hospital progress notes, laboratory reports, and diagnostics reports) related to the event.
- The Investigator will then record all relevant AE/SAE information in the CRF.
- As needed, the Sponsor/designee may ask for copies of certain medical records (e.g., autopsy reports, supplemental lab reports, documents on medical history/concomitant medications, discharge letters), as supporting source documentation. All participant identifiers, except the participant number, will be redacted on these copies before submission to the Sponsor/designee.
- The Investigator will attempt to establish a diagnosis of the event based on signs, symptoms, and/or other clinical information. Whenever possible, the diagnosis (not the individual signs/symptoms) will be documented as the AE/SAE.
- Specific guidance is in the CRF Completion and Monitoring Conventions.

Assessment of Intensity

The Investigator will assess the intensity of each AE and SAE reported during the study and assign it to 1 of the following categories:

- Mild: An event that is easily tolerated by the participant, causing minimal discomfort and not interfering with everyday activities.
- Moderate: An event that causes sufficient discomfort and interferes with normal everyday activities.

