- Severe: An event that prevents normal everyday activities. Do not confuse an AE that is assessed as severe with a SAE. Severe is a category used to rate the intensity of an event; both AEs and SAEs can be assessed as severe.

An event is defined as “serious” when it meets at least 1 of the predefined criteria specified in the definition of an SAE, NOT when it is rated as severe.

Assessment of Causality

- The Investigator will assess the relationship between study intervention and each AE/SAE occurrence:
 - Unrelated: Not reasonably related to the study intervention. AE could not medically (pharmacologically/clinically) be attributed to the study intervention. A reasonable alternative explanation will be available.
 - Related: Reasonably related to the study intervention. AE could medically (pharmacologically/clinically) be attributed to the study intervention.
- A “reasonable possibility” of a relationship conveys that there are facts, evidence, and/or arguments to suggest a causal relationship, rather than a relationship cannot be ruled out.
- The Investigator will use clinical judgment to determine the relationship.
- Alternative causes, such as underlying disease(s), concomitant therapy, and other risk factors, as well as the temporal relationship of the event to study intervention administration will be considered and investigated.
- The Investigator will also consult the IB and/or Product Information, for marketed products, in his/her assessment.
- For each AE/SAE, the Investigator will document in the medical notes that he/she has reviewed the AE/SAE and assessed causality.
- There may be situations when an SAE has occurred, and the Investigator has minimal information to include in the initial report to the Sponsor or its designee. To meet the reporting timeline, the causality assessment is not required for the initial report.
- The Investigator may change his/her causality assessment after considering follow-up information and send a SAE follow-up report with the updated causality assessment.

- The causality assessment is one of the criteria used when determining regulatory reporting requirements.

Follow-up of AEs and SAEs

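### Is the 50% stopping rule in Protocol 4.4 unworkable because Appendix 4 records causality on a different standard and for study intervention only?

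*Protocol*

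**What the plan says.** The second study termination criterion in Protocol Section 4.4 has two triggers. One is a single serious unexpected event suspected to be drug related. The other applies when at least 50% "of the participants show AEs of at least moderate severity", limited to events "for which a causal relationship to the study intervention or study-related procedures cannot be excluded". The causes covered are thus the intervention and the study procedures.

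Protocol Appendix 4 (Assessment of Causality) describes the recorded item: "The Investigator will assess the relationship between study intervention and each AE/SAE occurrence". There are two categories. The second opens "Related: Reasonably related to the study intervention". A further bullet explains that a reasonable possibility of a relationship means "there are facts, evidence, and/or arguments to suggest a causal relationship, rather than a relationship cannot be ruled out". Intensity is recorded separately as mild, moderate or severe, with a definition for each grade ("Moderate: An event that causes sufficient discomfort and interferes with normal everyday activities").

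For analysis, Protocol Section 9.4.2 states that "AEs will be tabulated and listed per participant and analyzed by severity and relationship to study intervention". SAP Section 15.1.1 splits related events into any, COC-related and evobrutinib-related, and counts a missing or unknown relationship as related. Neither section has a category for study procedures. Protocol Section 8.3 does mention procedures: it makes the investigator responsible for following up events thought to be related to them.

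**The concern.** The stopping rule and the recorded causality item differ in two ways. First, Section 4.4 counts events whose link cannot be excluded, whereas Appendix 4 asks for positive grounds, "rather than a relationship cannot be ruled out". Second, Section 4.4 covers procedures, and the Appendix 4 item does not. The opening of Section 6 defines study intervention as products or devices given to the participant, so a blood draw falls outside it. The risk table in Section 2.3.1 foresees fainting and hematoma from blood draws, and the schedule has 17 COC samples per profile on two occasions, or 34 draws per participant. A faint caused by a draw would properly be entered as Unrelated, yet it counts under Section 4.4 if it is moderate or worse.

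If someone monitored the rule by counting Related entries, the count could be too low and a stopping trigger could be missed. No special committee exists to settle the difference during the study.

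**Working it through.** **Inputs.** Threshold 50%, at least moderate severity (Protocol 4.4). Maximum of 20 participants (Synopsis). Recorded variables: intensity grade and Related/Unrelated to study intervention (Appendix 4). The 50% is a rule, so there is no derivation to reproduce.

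**Trigger count.** 0.5 × 20 = 10. With fewer participants it would be 9 of 18 or 8 of 16.

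**How far the two counts can differ.** Suppose 7 participants have a Related moderate or worse event and 4 others have a moderate event that is procedure-related or not excludable.
- From the Related field: 7/20 = 35%, no trigger.
- Under Section 4.4: (7 + 4)/20 = 11/20 = 55%, trigger.

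The arithmetic is right, but the 7 and the 4 are invented; the documents give no rate for such events in this setting.

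**What the recorded data do settle.** Let L be the number of participants with a Related moderate or worse event, U the number with any moderate or worse event, and C the count Section 4.4 needs. Every Related event qualifies, and no event below moderate does, so L ≤ C ≤ U. For 20 participants:
- L ≥ 10: the trigger is met.
- U < 10: the trigger is not met.
- L < 10 ≤ U: the U − L participants between the bounds must be judged one by one.

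In the example, taking U = 11, that means judging 4 participants.

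**How often the third case could arise.** It requires U ≥ 10, so its probability is at most P(U ≥ 10). Assume independent participants, each with probability p of any moderate or worse event. The value of p is an assumption, shown over a range:

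| p | P(U ≥ 10 of 20) |
|---|---|
| 0.20 | 0.003 |
| 0.30 | 0.048 |
| 0.40 | 0.245 |
| 0.50 | 0.588 |

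These are upper limits, because part of that probability belongs to L ≥ 10, where the trigger is already met. The undecided zone becomes likely only when about half of the participants have moderate or worse events of any cause.

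**The two causality texts side by side.** The bullet on reasonable possibility is stricter than Section 4.4. The category definitions above it are not clearly so. Unrelated is for an event that medicine offers no way to ascribe to the product and that has another reasonable explanation. Related is for one that may be so ascribed. An event whose link to the drug cannot be excluded does not fit Unrelated comfortably. On the intervention side, then, Appendix 4 gives two signals rather than a plain rejection of the Section 4.4 standard. On the procedure side the difference in scope is clear.

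**Can both sections be followed at once?** Yes. Section 4.4 does not name the Related field as the source of its count. The investigator can record causality by Appendix 4 and, separately, judge each moderate or worse event against Section 4.4. Section 8.3 already requires a view on procedure relatedness, because follow-up depends on it.

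**The case for a change.** The strongest reply is that a stopping rule should be verifiable. If the judgement required by Section 4.4 has no named place in the data, a monitor or inspector cannot reconstruct the count afterwards, and different staff could reach different totals. The SAP convention of counting missing or unknown as related does not help: it serves the final tables and leaves out procedures. The criterion of unacceptable risk is discretionary and does not make the numeric trigger countable.

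Most of this is fair as description. The scope mismatch stands, and neither document names a field for procedure relatedness. But two things limit its force. The case report form and its completion conventions are separate documents that are not available here, so the absence of such a field is not shown. And Appendix 4 requires the causality assessment for every event to be documented in the medical notes, so the source record from which a Section 4.4 count would be rebuilt does exist. A stopping rule may also be deliberately more cautious than a reporting classification; a difference between the two is not in itself an error.

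**Conclusion.** No change to the plan follows. Sections 4.4 and Appendix 4 differ in wording and scope, but they serve different purposes and can both be applied as written. No stated rule yields a wrong result. The exact Section 4.4 count may not be verifiable from the specified variables only when, with 20 participants, fewer than 10 have a Related moderate or worse event and at least 10 have any such event. Even then the cases to judge are few, and the participants are resident at one center from Day -1 to Day 18 under one investigator. Immediate safety concerns go to the sponsor at once under Section 8. The first criterion in Section 4.4 allows the study to be stopped for unacceptable risk or a worsened benefit-risk balance with no 50% count.

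The point has no effect on the primary comparison of AUC and Cmax or on any confidence interval. What remains is a gap in detail, namely where the Section 4.4 judgement is noted, which site and sponsor can fill in their working documents. The conclusion assumes that the investigator applies Section 4.4 directly and does not use a tally of Related entries in its place. Whether the two texts should read alike, and on which standard, is for the sponsor and investigator to decide.
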